Appendix 10: Clinical Assessment of Leg Ulcer

Chronic venous reference ulcer examination	
Localisation of the ulcer	(At baseline only)
Ulcer imaging	Picture taken Y/N
Observation of new ulceration	Y/N (Except at ASSE)
Complete healing	Y/N (Except at ASSE)
Wound bed % cover	Granulation tissue  Absent  Low (<10%)  Moderate (10 – 50%)  High (>50%)
	Fibrotic tissue  Absent  Low (<10%)  Moderate (10 – 50%)  High (>50%)
	Sclerotic tissue  Absent  Low (<10%)  Moderate (10 – 50%)  High (>50%)
Exudate	High, Moderate or Low
	Increasing of exudate level since last visit Y/N (Except at ASSE)
	Colour of the exudate (Serous, Haemoserous or Purulent)
	Odour Y/N
Surrounding skin appearance	Macerated Eczema Erythema Other (specify)
Signs of infection	Infection suspected (requiring systemic antibiotherapy): Y/N
	If Yes, Action taken
Ulcer treatment	Wound cleansing Y/N
	Debridement performed Y/N (Specify the method)
	Is the patient compliant to compression Y/N
	Local wound dressing: Hydrogel, Hydrocellular Foam, Alginate or Other (specify)

Appendix 11: Examples of Standard Meals

- Example of breakfast (around 600 Kcal):
 - 1 individual packet of cereal (28 grams or one ounce)
 - 2 slices of wholemeal bread
 - 2 slices of butter or low fat spread
 - 28 g Jam (or one ounce)
 - 250 ml semi skimmed milk
 - 240 ml Orange juice
- Example of lunch/dinner (around 1000 Kcal, well balanced with no more than 25% fat):
 - 100 g (or 3.5 ounces) beef or lamb or 160 g (or 5.6 ounces) of chicken / 250 g (or 8.8 ounces) of hake filet/ cooked with a small piece of butter
 - 100 g steamed potatoes / mashed potatoes / rice cooked
 - 100 g carrots
 - 100 g green beans
 - 100 g white bread
 - 1 nature yoghurt + 1 apple or 25 g (0.88 ounces) of gruyere
 - 250 ml of orangina or coca-cola or orange juice

Appendix 12: Ankle Brachial Pressure Index Form

Ankle Brachial Pressure Index (ABPI)

Inclusion criteria: $0.8 \leq \text{ABPI} \leq 1.3$

Systolic blood pressure will be measured after 10 minutes of rest **on both arms** in sitting position **or supine position** and **on each foot on the following 2 locations**: posterior tibial, and anterior tibial, following the procedure detailed in [Appendix 5](#) 'Ankle Brachial Pressure Index' of the study protocol.

Each measurement will be **performed twice** and completed in the following tables.

Brachial systolic blood pressure

	Measure 1 (mmHg)	Measure 2 (mmHg)
Right arm Systolic blood pressure		
Left arm Systolic blood pressure		

Ankle systolic blood pressure

	Location	Measure 1 (mmHg)	Measure 2 (mmHg)
Right ankle Systolic blood pressure	Posterior Tibial		
	Anterior Tibial		
Left ankle Systolic blood pressure	Posterior Tibial		
	Anterior Tibial		

Calculation of ABPI (Automatic calculation in eCRF)

$$\text{ABPI} = \frac{\text{Ankle systolic pressure} \\ (\text{Highest pressure of the ankle vessels for a leg})}{\text{Brachial systolic pressure} \\ (\text{Highest brachial pressure of the two arms})}$$

Document title

STATISTICAL ANALYSIS PLAN (SAP)

ATTACHED TO CL2-42909-016 STUDY

Study title

Dose-response relationship study of S42909 on leg ulcer healing after oral repeated administration in patients with active venous leg ulcer. A 10-week randomised, double-blind, placebo-controlled, prospective, international, multicentre, phase IIa study.

Test drug code

S42909

Indication

Venous leg ulcer

Development phase

IIa

Protocol code

CL2-42909-016

EudraCT Number

2016-004143-36

Universal Trial Number

NA

Sponsor

ILKOS THERAPEUTIC INC.

Date of the document

02 March 2020

Version of the document

1.0

CONFIDENTIAL

Signatories

Prepared by:

[name]
Biostatistician
Keyrus BioPharma – FRANCE

[figure not shown]
Signature

Date

02/03/2020

[name]
Biostatistician
I.R.I.S. – FRANCE

02/03/2020

Approved by:

[name]
Biostatistics Project Manager
I.R.I.S. – FRANCE

Signature

Date

[figure not shown]
02.03.2020

[name]
President and CEO
Ilkos Therapeutic Inc.

[figure not shown]
02/03/2020

[name]
Chief Medical Officer
Ilkos Therapeutic Inc.

[figure not shown]

02/03/2020

[name]
C.T.I.
I.R.I.S. – FRANCE

02/03/2020

Follow up of versions

Version	Release date (dd/mm/yyyy)	Key modifications (*)	Impact
1.0	02/03/2020	The linear advance of the wound margin towards the wound center will not be described as a relative change from baseline, as the value at baseline of the linear advance is equal to zero by definition. Only value at each visit will be provided.	No impact
		Additional subgroup : Size of the ulcer at baseline ($\leq 20 \text{ cm}^2$ / $> 20 \text{ cm}^2$)	No impact
		Randomised set definition: Only patients included will be considered.	2.1 Analysis sets
		MCPMod adjusted on diabetic factor and prognosis criteria on size and age of the ulcer at baseline will be provided as sensitivity analysis	3.4.2.2 Sensitivity analyses
		The primary analysis will be repeated in the FAS with patients from centers where PK results confirm the treatment intake.	3.4.2.2 Sensitivity analyses
		The number, dose and/or duration of analgesic drug for Venous Leg Ulcer (VLU) will not be described. The analgesic description will be done only through the question “Need to take medication for control of the pain associated with VLU?” from the pain questionnaire	3.4.3 Secondary efficacy criteria

Figure (1.3) 1 - Dose response models.....	13

List of abbreviations

%	: percentage
AE	: Adverse Event
ASSE	: Selection visit
ATC	: Anatomical Therapeutic Chemical
b.i.d.	: bis in die (twice a day)
BMI	: Body Mass Index
BP	: Blood Pressure
Bpm	: beats per minute (heart rate unit)
CHMP	: Committee for Medicinal Products for Human Use
CI	: Confidence Interval
cm	: centimetre
CPMP	: Committee for Proprietary Medicinal Products
CVD	: Chronic Venous Disease
DBP	: Diastolic Blood Pressure
e.g.	: exempla gratia (for example)
EAE	: Emergent Adverse Event
ECG	: ElectroCardioGram
e-CRF	: electronic-Case Report Form
EMA	: European Medicines Agency
FAS	: Full Analysis Set
FWER	: Family Wise Error Rate
g	: gram
G/L	: Giga (109) per litre
g/dL	: Gram per decilitre
h	: hour
HbA1c	: Glycated Haemoglobin
HR	: Heart Rate
i.e.	: id est
I.R.I.S.:	: Institut de Recherches Internationales Servier
ICH	: International Conference on Harmonization
IMP	: Investigational Medicinal Product
IS	: Included Set
IU	: International Unit
IWRS	: Interactive Web Response System
kg	: kilogram
L	: Litre
LLN	: Lower Limit of Normal laboratory reference range
LLS	: Lower Limit used to define potentially clinically Significant abnormal values
Max	: Maximum
MCPMod	: Multiple Comparison Procedures and Modeling
MED	: Minimal Effective Dose
MedDRA	: Medical Dictionary for Regulatory Activities
mg	: milligram
min	: minute
Min	: Minimum

mL	: millilitre
mm	: millimetre
mmHg	: millimetre of mercury
ms	: millisecond
NA	: Not Applicable
NAE	: Number of Adverse Events
NEAE	: Number of Emergent Adverse Events
ng	: nanogram
NPD	: Number of Protocol Deviations
o.d.	: omni die (every day)
PCSA	: Potentially Clinically Significant Abnormal value
PD	: Pharmacodynamics
PK	: Pharmacokinetics
po	: per os (orally)
PPS	: Per Protocol Set
PT	: Preferred Term
PV	: PharmacoVigilance
QTc	: QT interval corrected for heart rate
RBC	: Red Blood Cells
RS	: Randomised Set
RU	: Reference Ulcer
s	: second
SAE	: Serious Adverse Event
SAP	: Statistical Analysis Plan
SBP	: Systolic Blood Pressure
SD	: Standard Deviation
SEAE	: Serious Emergent Adverse Event
SOC	: System Organ Class
SS	: Safety Set
t.i.d.	: ter in die (three times a day)
TLG	: Tables, Listings and Graphs
TU	: Therapeutic Unit
ULN	: Upper Limit of Normal laboratory reference range
ULS	: Upper Limit used to define potentially clinically Significant abnormal values
VAS	: Visual Analog Scale
VLU	: Venous Leg Ulcer
WHO	: World Health Organization

1. INTRODUCTION

This Statistical Analysis Plan (SAP) details the planned analyses to be performed, in accordance with the main characteristics of the amended study protocol (version N° 4 dated 05 March 2018).

The templates for Tables, Listings and Graphs (TLG) are described in a separate document.

Of note, this SAP does not cover the pharmacokinetic and metabolism profiling and genomic assessment and non genomic biomarkers data analyses described in the study protocol. These analyses are covered in separate analysis plans.

1.1. Study objectives

The purpose of this study is to investigate if S42909 at any dose has an effect on healing of venous leg ulcer (VLU) (proof of concept) and to explore the relationship between dose and effect of S42909 on venous leg ulcer healing on top of standardized compression and local wound care.

The primary objective is to detect the existence of an overall dose-response relationship with S42909 on improving healing of venous leg ulcers on top of standard of care (compression and local wound care) after 4 weeks of treatment.

The secondary objectives are:

- To determine a dose window for the Minimal Effective Dose (MED) on improving healing of venous leg ulcers.
- To explore the effect of S42909 on improving healing of venous leg ulcers on top of standard of care (compression and local wound care) after 6 weeks of treatment.
- To explore the effect of S42909 on improving pain related to venous leg ulcer over 6 weeks.
- To explore the effect of S42909 on decreasing analgesic drug consumption related to venous leg ulcer over 6 weeks.
- To assess the safety profile of each tested dose of S42909 (adverse events, laboratory parameters, physical examination, body weight, vital signs (blood pressure, heart rate), 6 or 12-lead electrocardiogram (ECG) and standard urinalysis).
- To assess the pharmacokinetics (PK) of S42909 and its metabolites in patients after repeated administration of S42909.

The additional objectives are:

- To assess any potential PK/Pharmacodynamics (PD) relationship (mainly on improving healing of venous leg ulcers and pain related to venous leg ulcer).
- Genomic assessment of S42909.
- To collect the blood for non genomic biomarkers which can be related to venous leg ulcer healing, underlying chronic venous disease, response to S42909 treatment (bio-collection in a bio-repository).

1.2. Study design

Study CL2-42909-016 is a Phase IIa, prospective, international, multicentre, randomised, double-blind, placebo-controlled, parallel group (S42909: 100, 200, 400, 800 or 1200 mg per day and placebo), dose-finding study in patients with venous leg ulcers.

1.2.1. Study plan

The study is divided into the following three periods:

- A placebo run-in period of 14 days (from the selection visit (ASSE) to the inclusion/randomisation visit at week 0 (W000)), in which patients are investigated for documenting the presence of Chronic Venous Disease (CVD) and for assessing the type and the size of the Reference Leg Ulcer.
- A double-blind treatment period of 6 weeks (from visit 0 (W000) to visit 6 (W006)) on top of standard of care (standardized compression and local wound care with sterile saline solution or sterile water and “non-active” dressing):

[figure not shown]
At W000:

- Patients are randomised to one of the following six groups – S42909: 100, 200, 400, 800 or 1200 mg per day - or placebo.
- Note that the treatment (S42909 or Placebo) post randomisation is considered as Investigational Medicinal Product (IMP).
- For each group, patients are instructed to take 3 tablets orally (per os administration) twice a day at the end of the meals in the morning and in the evening. The appearance and taste of the tablets are the same for all IMPs throughout the study.
- The first IMP intake takes place the day of the inclusion visit (W000).
- A follow-up period of 2 weeks without treatment (from visit 6 (W006) to visit 8 (W008)).

During this period, patients continue to receive the standard of care only.

The study plan is shown in Figure (1.2.1) 1.

Figure (1.2.1) 1 - Study plan

1.2.2. Type of randomisation

The treatment randomisation and allocation are centralised using an Interactive Web Response System (IWRS) procedure. The treatment (S42909: 100, 200, 400, 800 or 1200 mg per day or placebo) is assigned at the inclusion visit (W000) by a dynamic, balanced with 1:1:1:1:1 ratio, stratified randomisation according to the country, a combined prognosis criteria (size and age of ulcer) and diabetic status (yes/no). The randomisation algorithm is built according to an adaptive randomisation by minimisation.

The combined prognosis criteria (size and age of ulcer) for ulcer healing are:

- A: $\leq 10 \text{ cm}^2$ and $\leq 6 \text{ months}$.
- B: $> 10 \text{ cm}^2$ or $> 6 \text{ months}$.

For the randomisation, the diabetic status is defined by known diabete and/or a fasting blood sugar $\geq 7 \text{ mmol/L}$ and/or elevated HbA1c value between 6.5% and 8% on pre-inclusion laboratory results.

Participants in the optional 24-hour PK analysis are distributed across treatment arms.

[figure not shown]
1.3. Determination of sample size

Sample size was estimated with a type one error rate set at 2.5% and using the statistic function “sampszie” described in the publication “MCPMod: An R Package for the Design and Analysis of Dose-Finding Studies” edited by B. Bornkamp, J. Pinheiro and F. Bretz (2009).

Considering:

- A standard deviation of 42%.
- A minimal relative change of Reference ulcer area at 4 weeks (Rmin) of 32.5%.
- A maximal relative change of Reference ulcer area at 4 weeks (Rmax) of 62.5%.
- A maximal efficacy (Rmax – Rmin) of 30%.
- Six doses: 0 (placebo), 100, 200, 400, 800, 1200 mg per day.
- Seven candidate models defined by some couples (d*, p*) (dose, maximal percentage of efficacy):
 - Linear.
 - Emax1 (200 mg, 90%).
 - Emax2 (400 mg, 70%).
 - Sigmoid Emax (200 mg, 10%) and (1000 mg, 90%).
 - Logistic (200 mg, 10%) and (1000 mg, 90%).
 - Exponential1 (400 mg, 10%).
 - Exponential2 (800 mg, 10%).

Candidate models are presented in [Figure \(1.3\) 1](#).

Figure (1.3) 1 - Dose response models

- Function “min” of Bretz package (power of each model is greater or equal to the nominal power to detect a signal of dose-response relationship).

27 evaluable participants per group guarantee a nominal power of at least 80% to detect a signal of dose-response relationship (proof-of-concept).

After 1000 data simulations based on above hypotheses, with a true dose-response relationship supposed to be a logistic model (defined by the couples (200 mg, 10%) and (1000 mg, 90%)) and 27 participants by dose, the empiric power to detect a signal of dose-response relationship (main objective) is about 90%.

Taking into account an exclusion rate from the Randomised Set (RS) estimated at 20%, about 34 participants per treatment group had to be included.

Based on that exclusion rate, a total of 204 patients was planned to be included in the study. Due to recruitment difficulties, 121 patients were finally included in the study.

2. ANALYSIS SETS / TREATMENT GROUPS

2.1. Analysis sets

- Randomised Set (RS):

All included and randomised patients (*i.e.* all patients to whom a Therapeutic Unit (TU) was randomly assigned using IWRS).

- Safety set for double blind period (SS):

All patients having taken at least one dose of IMP.

Note: Patients for whom no information is available about any IMP intake, will be excluded from the Safety Set if they have no post-baseline safety assessment.

- Full Analysis Set (FAS):

In accordance with the intention-to-treat principle and Section 5.2.1 of the [ICH E9](#) guideline, all randomised patients who received at least one dose of IMP and who have at least one baseline value and one value of Reference ulcer (RU) area (primary efficacy criterion) at W004.

- Per Protocol Set (PPS):

All patients of the Full Analysis Set (FAS) without relevant deviation(s) which could affect the evaluation of the IMP effect on the primary efficacy criterion. The deviations are categorized in three groups, as follows:

* : According to protocol deviation

**: According to medical review

□ : Derived in datasets

More precisely, the PPS includes all patients of the FAS with:

Before/at inclusion (all Caucasian patients of the FAS) with:

- BMI at ASSE between 18.5 and 45 kg/m² inclusive*.
- RU localised in the gaiter area. RU diagnosed or reoccurred for more than 6 weeks and less than 2 years at ASSE*.
- Size of RU $\geq 5 \text{ cm}^2$ and $\leq 100 \text{ cm}^2$ in the picture taken at the selection visit (ASSE) (or ASSE-R), as measured by 3D imaging device*.
- Size of RU $\geq 4.5 \text{ cm}^2$ and $\leq 100 \text{ cm}^2$ at picture taken before inclusion (W000).□
- Change in RU area < 20% between picture taken at ASSE (or ASSE-R) and the picture taken 3 or 4 days before inclusion (W000) *.
- Ankle Brachial Pressure Index ≥ 0.8 and ≤ 1.3 *.
- Patients with chronic venous disease documented by Duplex Scan (during the selection period, or within 6 months before selection), with a venous reflux in the superficial and/or deep veins and/or a venous obstruction in the deep veins*.
- Required Laboratory values (authorized).
 - Serum albumin $\geq 20 \text{ g/l}$.
 - Hb $\geq 10 \text{ g/dL}$ *
 - HbA1c $\leq 8\%$ (either from a test done within 3 months before selection or during the selection period)*.

Before/at inclusion (all Caucasian patients of the FAS) without:

- Unauthorized diseases**:
 - Presence of malabsorption disease (Crohn's disease), inflammatory bowel disease, Gilbert syndrome, history of chronic diarrhoea.
 - History of lower extremity deep venous thrombosis within the last 3 months.
 - Known major cardiovascular events (acute coronary syndrome including unstable angina and myocardial infarction, stroke) within 6 months prior to the study or congestive heart failure Class III-IV within 6 months prior to the study.
- Unauthorized diseases*:
 - Other non-venous leg ulcers or other associated skin conditions: vasculitis, malignancies, burns, post-surgery, pressure ulcers, diabetic foot, connective tissue disorders such as lupus, systemic sclerosis, cellulitis, ulcers due to sickle-cell disease.
 - History of major abdominal surgery which in the investigator's opinion could interfere with the absorption, metabolism of the drug (e.g. gastro-intestinal resection, intestinal anastomosis or shunt).
- Unauthorized treatments**:
 - Participants who are undergoing treatments known to affect healing within the month prior to selection: pentoxifylline, immunosuppressive drugs, immunomodulators, cytotoxic chemotherapy or oral corticosteroids.
 - Topical corticosteroids application on and around the ulcer within 15 days prior to selection.
 - Participants who have been exposed to venoactive drugs within the month prior to the selection.
 - Participants on oral or parenteral antibiotic therapy. Long-term, low dose prophylactic antibiotic therapy started at least one month prior to the selection is however acceptable if there is no change in the treatment during the study.
- Planned surgery and venous procedures (including vein stripping, foam sclerotherapy or any endovenous procedure) on the leg with the Reference venous leg ulcer during the study period **.

During the W000 - W004 period with:

- Blind not broken.
- Received treatment = planned treatment (IWRS).
- Duration of Study Treatment between 26 and 30 days (inclusive).
- Compliance with Study Treatment should be between 80% and 120%.
- Compliance with compression stockings should be \geq 80%.

During the W000 - W004 period without:

- Unauthorized concomitant treatment**:
 - Topical corticosteroid application on and around the ulcer.
 - Oral corticosteroids.
 - Immunomodulators, immunosuppressants, cytotoxic chemotherapy.
 - Pentoxifylline.
 - Venoactive drugs within the month prior to selection and during the study.
 - Participants on oral or parenteral antibiotic therapy. Long-term, low dose prophylactic antibiotic therapy started at least one month before the selection is however acceptable if there is no change in the treatment during the study.

- Local antibiotherapy on the surface of RU.
- Oral and parenteral antibiotherapy during the study, except if less than or equal to 7 days.
- Withdrawal criteria:
 - Clinically significant anemia defined by an haemoglobin level < 10g/dL and a decrease ≥ 1.5 g/dL in men and ≥ 1 g/dL in women compared to previous value. ☒

The size of each analysis set and reasons for exclusion of patients will be described.

Listings of patients with their membership, or not, in each analysis set and of excluded patients with reasons for exclusion will be provided.

Listing of patients randomised but non included patients will be provided.

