The participants will enter a 6-week ambulatory IMP treatment period on top of standard of care (standardized compression and local wound care with sterile saline solution or sterile water and “non-active” dressing) followed by a 2-weeks follow-up period with standard of care only. During this period the participants will return to the investigator’s site for intermediate visits after one week (W001), two weeks (W002), three weeks (W003), four weeks (W004), six weeks (W006) and eight weeks (W008). Participants will continue to receive standardized compression therapy and local wound care (sterile saline solution or sterile water and “non-active” dressing) until the end of the study (W008). At W000, W004 and W006 visits, pain assessment will be performed at the beginning of the visit using a questionnaire with VAS. At each visit, the clinical features of the RU will be recorded and a 3D picture of the RU will be taken after wound bed preparation. All 3D pictures will be recorded and uploaded for central review, measurement of ulcer area, perimeter and volume for the primary and secondary endpoints of the study.

Four PK samples will be taken at W000, W004 and W006 visits and one predose PK sample will be taken at W001 and W002 visits in all participants. The participants who agreed to participate in the optional PK analysis in participating centres (7 patients per dose group) will have 9 PK samples collected over 12 hours at W000 visit and 13 PK samples collected over 24 hours at the W004 visit instead of the 4 PK samples.

At each visit general compliance with standardized compression will be checked and size of the stockings will be adjusted, if needed. The participant should be explained that the standardized compression stockings should be worn everyday and used according to the recommendations given by the investigator.

- If complete healing of the reference ulcer is observed during the study conduct but other ulcers are still open, the participant will keep the same standardized compression until complete healing of all ulcers is observed or until the end of the study and will continue to take IMP treatment until W006 visit.

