- If complete healing of all ulcers (including the reference ulcer) is observed, the participant will keep the same standardized compression until the end of the study or be switched to a compression for leg ulcer recurrence prevention (> 18 mmHg) if the participant refuses (this type of compression will not be provided to the sites). The participant will continue to take the study drug until W006.

The end-of-study visit is scheduled to take place at W008 or, in case of prematurely withdrawn participants as soon as possible, after stopping the use of standardized compression, or after the last IMP intake. In case of premature withdrawal, the next expected visit will be performed. If the next expected visit is W003, biochemistry and haematology should be added to the assessments to be performed during this visit.

An electronic case report form (e-CRF) will be used for data capture during the study.

[figure not shown]
The study plan is shown in [Figure \(4.2.1\) 1.](#)

Figure (4.2.1) 1 - Study plan**- Treatment periods-**

Placebo	Group A	S42909 dose 100 mg, p.o., 50 mg bid	N=34
	Group B	S42909 dose 200 mg, p.o., 100 mg bid	N=34
	Group C	S42909 dose 400 mg, p.o., 200mg bid	N=34
	Group D	S42909 dose 800 mg, p.o., 400 mg bid	N=34
	Group E	S42909 dose 1200mg, p.o., 600mg bid	N=34
	Group F	Placebo, p.o., bid	N=34

← On top of standard of care (standardized compression and local wound care)

Study periods

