5.6. Participant withdrawal

5.6.1. Withdrawal criteria

Information to be collected during the last visit of these participants is given in [section 5.6.2](#). These follow-up modalities are used to ensure the efficacy and safety evaluation of all participants who received the IMP.

The reasons for premature discontinuation of IMP are:

- Adverse events or any condition that would jeopardise participants' safety and is incompatible with continuation of the IMP according to the judgement of the investigator. These include:
 - **ALT or AST increase > 3 times the ULN value**, after 2 consecutive tests performed 7 days apart.
 - **Total bilirubin increase > 2 times the ULN value**, after 2 consecutive tests performed 7 days apart.
 - **CPK increase > 5 times the ULN value**, after 2 consecutive tests performed 7 days apart.

- **Clinically significant anaemia** defined by an haemoglobin level < 10g/dL and a decrease ≥ 1.5 g/dL in men and ≥ 1 g/dL in women compared to previous value.
- **QTcF > 500 ms, or QTcF > 480 ms with increase in QTcF > 60 ms as compared with QTcF at selection period**, confirmed by a repeated ECG, with measurements validated by a cardiologist.
- Clinically significant adverse event related to the cardiovascular system for which, in the judgement of the investigator, continuation of the IMP could constitute a risk for the safety of the participant.
- **Severe uncontrolled diarrhoea with risk of dehydration.**
- **Major deviation to the protocol or any medical condition incompatible with continuation of the IMP treatment** (including pregnancy) **or preventing the analysis of the primary endpoint** (e.g. non-compliance with standardized compression regimen or with protocol requirements or study-related procedures).
- Any medical event requiring administration of an unauthorised concomitant treatment (see [section 6.3](#)).
- **Non-medical reason** (e.g. withdrawal of participant's consent), which should be carefully documented.
- **Lost to follow-up** (see [section 5.6.3](#)).

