The previous treatments are the treatments for venous leg ulcers taken within 6 months before selection, or any previous treatments which could interfere with the IMP or the study assessments in the last 6 weeks before the selection with associated stop date strictly inferior to the first IMP intake date (W000).

Note: In case of patient included and/or randomised but not treated (*i.e.* patients with treatment duration equal to 0), the previous treatment is defined as any treatment with an associated stop date strictly inferior to the date of the inclusion visit.

Only treatment with an Anatomical Therapeutic Chemical (ATC) classification and/or a Preferred name is considered.

No specific previous treatments are defined.

The compliance of compression stocking

The compliance of compression stocking (%) for each period (W000-W004 and W000-W006 periods) is defined as:

(Sum of number of days of stockings wearing / Sum of number of days when stockings had to be worn) x 100 (for the considered period)

with:

- Number of days of stockings wearing = Number of days of stockings wearing.
- Number of days when stockings had to be worn = Last visit date - First visit date, in days (for the considered period)

Note: Compliance is not calculated in case of missing information.

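### The PPS stocking-compliance rule can exclude early complete healers for a compression switch that the protocol permits

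*SAP*

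**What the plan says.** Protocol 4.2.1 covers patients in whom every ulcer has healed. By default they keep the study compression. The alternative is to "be switched to a compression for leg ulcer recurrence prevention (> 18 mmHg) if the participant refuses", and the protocol adds that "this type of compression will not be provided to the sites". IMP continues to W006 either way. The option is narrow. "If complete healing of the reference ulcer is observed during the study conduct but other ulcers are still open", the study compression is kept and no switch is offered.

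SAP 2.1 lists the PPS conditions for W000-W004. One is that "Compliance with compression stockings should be" at least 80%. It makes no exception for healed patients. In the text available, the line also lacks the medical-review mark that some other PPS conditions carry.

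SAP 5.2.1 defines compliance as days worn divided by days due, with "Number of days when stockings had to be worn = Last visit date - First visit date, in days". The denominator does not stop at healing or at the switch, and nothing says whether days in the replacement compression count as worn. Protocol 6.4 takes the days worn from the participant's diary.

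The primary analysis is in the FAS (SAP 3.4.2.1). The PPS is used for a supplementary repeat of it (3.4.2.3) and for descriptions of the secondary efficacy criteria (3.4.3).

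**The concern.** A patient who uses the option in protocol 4.2.1 is following the protocol. The SAP formula nevertheless scores that patient as non-compliant from the day of the switch, and the PPS rule then removes a case with no deviation behind it.

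The removal is linked to the endpoint. Only patients with all ulcers healed before W004 can switch and, if still healed at W004, they have the best possible value of the primary criterion. A per-protocol set should not lose patients because they did well. If effective doses produce enough extra early healers, the PPS repeat would show a flatter dose-response than the FAS for a reason unrelated to adherence.

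**Working it through.** **Plan's own figures.** The documents give no figure for this point. The illustration in step 3 borrows the sample-size assumptions (SD 42; mean reductions 32.5% and 62.5%; 27 evaluable per group). These reproduce: simulating the seven-model contrast test at one-sided 2.5% gives a lowest power of 81.5% at 27 per group and 79.8% at 26. Then 27/0.8 = 33.75, rounded to 34, and 34 x 6 = 204.

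**Step 1: the rule on a 28-day period.** 0.8 x 28 = 22.4, so at least 23 days must be worn. Six or more days out of the study stockings fails. For a patient fully adherent until the switch:

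| Switch at | Nominal compliance | Range over visit windows (W004 at day 26 to 30) |
|---|---|---|
| W001 | 7/28 = 25% | always fails |
| W002 | 14/28 = 50% | at most 17/26 = 65.4%; always fails |
| W003 | 21/28 = 75% (22/28 = 78.6% if the visit day counts) | 19/30 = 63.3% to 24/26 = 92.3%; may pass |

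The maxima count the visit day as worn. The 26 to 30 days follow the treatment-duration condition in SAP 2.1.

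**Step 2: direction.** Removing a fraction a of an arm with mean m, each removed patient at 100%, lowers the arm mean by a/(1-a) x (100-m). With 121 patients included, there are about 121/6 = 20 per arm. One or two removals take a mean of 62.5% to (1250-100)/19 = 60.5% or (1250-200)/18 = 58.3%. One removal from a placebo arm at 32.5% gives (650-100)/19 = 28.9%, a larger fall. The difference therefore shrinks only if a/(1-a) in the dose arm exceeds 67.5/37.5 = 1.8 times its value on placebo.

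**Step 3: illustrative upper bound.** Under normality, the share at or above 100% reduction at W004 is 18.6% for mean 62.5 and 5.4% for mean 32.5. Capping at 100 gives means of 58.2 and 31.5, a difference of 26.7 points. Assume a fraction f of these healers is excluded, equal in both arms (the documents give no value):

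| f | Difference (points) |
|---|---|
| 0.10 | 26.3 |
| 0.25 | 25.6 |
| 0.50 | 24.3 |
| 1.00 | 21.1 |

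The SD falls too. The standardised difference goes from 0.71 to 0.70 at f = 0.10 and 0.69 at f = 0.25.

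**Step 4: after the fix.** If numerator and denominator both end at the switch, the patients in step 1 score 7/7, 14/14 or 21/21 = 100% and stay in the PPS.

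**The case against.** The strongest reply is that this will rarely happen. The default is to keep the study stockings. A switch needs every ulcer healed, healing seen by about W003, and refusal by the patient. Entry requires at least 4.5 cm² and no more than 20% change over run-in, and protocol section 2 says healing under standard care may take 6 months or more. The PPS is supplementary, protocol 10.1.3 allows exclusion criteria to be updated before unblinding, and a blind review is planned (protocol 14.2). If replacement-compression days were counted as stocking days, the problem would vanish. All of this stands and limits the size. It does not remove the gap, because the SAP states a numerical rule without exception and does not say that replacement days count.

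Two stronger readings are tempting but unsupported:

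- A reader might infer that switching triggers the end-of-study visit, because protocol 4.2.1 times that visit "after stopping the use of standardized compression, or after the last IMP intake". That clause concerns participants already prematurely withdrawn. A permitted switcher who stays on IMP is not one of them.
- A reader might infer that protocol 5.6.1 forces such a patient off IMP, since it mentions "non-compliance with standardized compression regimen or with protocol requirements or study-related procedures". There it is an example under major deviations, or conditions incompatible with continued IMP or preventing analysis of the primary endpoint. A switch allowed by 4.2.1 is not obviously any of these. The wording needs reconciling, but it is not a direct contradiction.

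**Conclusion.** The point holds as a minor defect in the PPS definition. Taken literally, the SAP excludes an otherwise adherent complete healer who makes the permitted switch at W001 or W002, and on the nominal schedule at W003 as well. This assumes that stockings means the study stockings, which is the plain reading but is not stated.

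The number affected is unknown and probably small. The primary FAS analysis is not affected.

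The range of 26.3 to 21.1 points, against 26.7 with nobody excluded, should not be read as an expected effect. The 18.6% and 5.4% are tail shares for the reference ulcer at W004. Exclusion needs all ulcers healed earlier, plus refusal, and patients first healed at W004 cannot be affected. The lower end is therefore a bound, not a plausible scenario. Nor do the documents support saying that the bias always runs against an effective dose. It does so only if healers are removed sufficiently more often at effective doses, as step 2 shows.

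**What to change.** In SAP 2.1 and 5.2.1, state that a stocking shortfall arising only after a switch permitted by protocol 4.2.1 does not exclude a patient from the PPS. Either count those days as compliant, or end both numerator and denominator at the documented switch or at healing of all ulcers. Do not cut at reference-ulcer healing alone, because patients with other open ulcers must keep the study compression.

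Identify these patients at the blind review, before unblinding. The complete-healing item in protocol Appendix 10 sits on the reference-ulcer form, so an all-ulcer healing date may need checking against source. The documents do not say that days in the replacement compression are recorded.

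Separately, ask the sponsor to reconcile the non-compliance wording in protocol 5.6.1 with the option in 4.2.1.

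The cost is one SAP rule, a small programming change and a small blinded case review.
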